be incurable. It is important that, until aggressive treatment for oligometastatic disease becomes standard of care, careful attention is paid to the quality of life in treated patients. Multiple validated QOL surveys are available for a variety of cancer sites. Collection of such surveys will help to monitor the impact of treatment on QOL.

To our knowledge, there have not been any prospective trials examining the role of aggressive therapy in the treatment of oligometastatic disease only at initial presentation. None of the previously described reports include only patients at initial presentation; the majority of patients in the prospective and retrospective oligometastatic studies have had previous therapy. In order to better evaluate the role of curative therapy in patients presenting with oligometastatic disease we are proposing a prospective study of this patient cohort. Patients with oligometastatic disease (defined for this study as 5 or fewer sites of disease involving 3 or fewer organ systems) will receive SRS/SBRT to all sites of oligometastatic disease and standard curative therapy to the primary disease. The primary objective for this study will be feasibility with the potential for an eventual phase III study. In addition, clinical and translational information will be collected to better stratify patients with oligometastatic disease for future studies.

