10.3 Evaluation after study

10.3.1 Patients will be seen in follow-up with study physicians 6 weeks after completion of SRS/SBRT and then at 3 month intervals for 3 years and 6 months thereafter.

10.3.2 QOL survey to be performed prior to therapy, after SRS/SBRT and at subsequent follow-up visits using the FACT-G survey. See Appendix IV.

10.3.3 Toxicity will be evaluated after the study using Common Cancer Toxicity Criteria V 4.0

10.3.4 Follow-up imaging should be performed at least every 3 months for the first two years from completion of therapy and every 6 months afterwards until five years from the completion of therapy. FDG-PET/CT scan for follow-up is recommended but not required.

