11.0 STATISTICAL CONSIDERATIONS

Primary objective: Delivery of SBRT to multiple sites in a safe and effective manner with acceptable toxicity

Primary Endpoint(s):

- Presence of multiple sites (between 2 and 5 sites)
- Acceptable toxicity: Grade 3 or less

Secondary objectives/Endpoints:

- Quality of life (as measured by the FACT quality of life surveys, see appendix IV)
- Local control of metastatic sites
- Local control of primary site
- Overall survival (OS), Two-year Overall Survival
- Analysis of patterns of failure post-SRS/SBRT (subsequent sites of failure and time to failure)

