11.2 Sample size

Phase II studies are usually small trials, recruiting participants up to about 20, although often a lot less. However, we plan to analyze the data stratified by different primary cancer such as breast, prostate, and etc., since we are trying to detect which patient subsets are most likely to benefit from the proposed treatment. The sample size can be set at approximately 10 for each patient subset in order to have a reasonable estimate of overall survival, local control, and quality of life for each subset. We estimate that most of the patients will have breast, lung, and prostate primaries and that there will be smaller numbers with other primary types. Based on these assumptions, we estimate a sample size of 40 patients and expect a 10% drop-out rate and thus have set an estimated sample size of 44 patients.

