11.3 Data analysis

Two-year survival rate will be calculated for all the patients and each patient subset respectively by using Kaplan-Meier survival analyses, with survival and event times defined from the day of enrollment until either an event or last follow-up. We can compare these two year survival rates with those from the patients using traditional therapy. Median overall survival will also be estimated.

Univariate survival analysis will be performed to identify the statistically significant variables, using Log-Rank test or univariate Cox proportional hazard regression based on the data type of predictor variables. Significant ($P < .05$) variables on univariate analyses will then be tested with multivariate analyses by using Cox proportional hazard regression model (Milano MT, et al., 2007).

Quality of life outcomes will be analyzed by using univariate and multivariate logistic regression successively and the quality of life will be coded as "improved" or "non-improved".

We will also report the entire patient characteristics at initial presentation of oligometastatic disease and characteristics of Long-term (≥ 2 years) survivors by using descriptive statistics.

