Appendix IV - Sample of QOL form (FACT-G)

FACT-G (Version 4)

Below is a list of statements that other people with your illness have said are important. Please circle or mark one number per line to indicate your response as it applies to the past 7 days.

PHYSICAL WELL-BEING		Not at all	A little bit	Some-what	Quite a bit	Very much
GP1	I have a lack of energy	0	1	2	3	4
GP2	I have nausea	0	1	2	3	4
GP3	Because of my physical condition, I have trouble meeting the needs of my family	0	1	2	3	4
GP4	I have pain	0	1	2	3	4
GP5	I am bothered by side effects of treatment	0	1	2	3	4
GP6	I feel ill	0	1	2	3	4
GP7	I am forced to spend time in bed	0	1	2	3	4
SOCIAL/FAMILY WELL-BEING		Not at all	A little bit	Some-what	Quite a bit	Very much
GS1	I feel close to my friends	0	1	2	3	4
GS2	I get emotional support from my family	0	1	2	3	4
GS3	I get support from my friends	0	1	2	3	4
GS4	My family has accepted my illness	0	1	2	3	4
GS5	I am satisfied with family communication about my illness	0	1	2	3	4
GS6	I feel close to my partner (or the person who is my main support)	0	1	2	3	4
Q1	Regardless of your current level of sexual activity, please answer the following question. If you prefer not to answer it, please mark this box  and go to the next section.					
GS7	I am satisfied with my sex life	0	1	2	3	4

FACT-G (Version 4)

Please circle or mark one number per line to indicate your response as it applies to the past 7 days.

EMOTIONAL WELL-BEING		Not at all	A little bit	Some- what	Quite a bit	Very much
GE1	I feel sad.....	0	1	2	3	4
GE2	I am satisfied with how I am coping with my illness.....	0	1	2	3	4
GE3	I am losing hope in the fight against my illness.....	0	1	2	3	4
GE4	I feel nervous.....	0	1	2	3	4
GES	I worry about dying.....	0	1	2	3	4
GE6	I worry that my condition will get worse.....	0	1	2	3	4

FUNCTIONAL WELL-BEING		Not at all	A little bit	Some- what	Quite a bit	Very much
GF1	I am able to work (include work at home)	0	1	2	3	4
GF2	My work (include work at home) is fulfilling.....	0	1	2	3	4
GF3	I am able to enjoy life.....	0	1	2	3	4
GF4	I have accepted my illness.....	0	1	2	3	4
GF5	I am sleeping well	0	1	2	3	4
GF6	I am enjoying the things I usually do for fun.....	0	1	2	3	4
GF7	I am content with the quality of my life right now.....	0	1	2	3	4

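### The one specified quality-of-life analysis pools preserved with worsened FACT-G scores, so it should be supplemented by a three-category table and a mean-change summary

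*Combined protocol and SAP*

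**What the plan says.** QOL is a secondary endpoint (sections 2.0 and 11.0), measured with the FACT-G. Section 1.0 explains why it is collected: until aggressive treatment of oligometastatic disease is standard, it is important that "careful attention is paid to the quality of life in treated patients", and "Collection of such surveys will help to monitor the impact of treatment on QOL".

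The forms are serial. Section 10.3.2 reads: "QOL survey to be performed prior to therapy, after SRS/SBRT and at subsequent follow-up visits using the FACT-G survey". Section 10.3.1 sets the first follow-up visit at 6 weeks after completion of SRS/SBRT, with further visits every 3 months for 3 years.

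The analysis is in section 11.3. The method is logistic regression, first with single predictors and then with several. The outcome has two levels: "the quality of life will be coded as 'improved' or 'non-improved". No change threshold and no visit are attached to that code. The descriptive statistics in the same section cover patient characteristics and the characteristics of long-term survivors; QOL is not named there.

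Section 11.2 also mentions QOL. It sets about 10 patients per primary-cancer subset "in order to have a reasonable estimate of overall survival, local control, and quality of life for each subset". This states an intent to estimate QOL by subset but gives no scale, summary or method.

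**The concern.** A patient who keeps a baseline level of QOL through SBRT and definitive treatment of the primary has had a good result. A patient whose QOL falls has not. The planned code puts both in the same level. In a single-arm study there is no concurrent group whose improved rate would help a reader judge the number.

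Monitoring the impact of treatment has to cover impact in both directions. If the plan is followed as written, the report gives the proportion improved and the factors associated with improvement. It does not say how many patients got worse. The study is meant to inform a possible phase III trial, and the burden of an aggressive strategy on patients is something the planners of that trial would want to read from it.

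**Working it through.** **The plan's own figure.** Section 11.2 takes 40 patients and 10% drop-out to 44: 40 × 1.10 = 44, which reproduces. No part of this calculation is tied to QOL, and nothing below changes it. The 40 is used here only as a denominator.

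**What the code identifies.** Let n patients have usable forms, of whom a improve, s are stable and w worsen, so a + s + w = n. The planned analysis uses a and n − a = s + w only. Given a, w can be any number from 0 to n − a. The split of s + w is not recoverable from the coded result.

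**Illustration.** The documents give no QOL rates, so the counts are assumed, and all 40 patients are taken to have usable forms. Intervals are exact (Clopper-Pearson): lower limit = Beta quantile 0.025 with parameters (x, n − x + 1); upper limit = Beta quantile 0.975 with parameters (x + 1, n − x).

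| | Case A | Case B |
|---|---|---|
| Improved / stable / worse | 12 / 24 / 4 | 12 / 4 / 24 |
| Planned result: improved | 12/40 = 30% (16.6-46.5%) | 12/40 = 30% (16.6-46.5%) |
| Not shown by the plan: worsened | 4/40 = 10% (2.8-23.7%) | 24/40 = 60% (43.3-75.1%) |

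The planned proportion is identical in the two cases. The intervals for the worsened share do not overlap, so a three-category table would tell the cases apart even at this sample size.

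**Precision of an added mean-change summary.** The documents give no standard deviation for FACT-G change, so the half-width of the 95% CI for unadjusted mean change is expressed in SDs of change: t(0.975, n − 1) / √n.

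- n = 40 (every patient returns a form): 2.023 / 6.325 = 0.32 SD
- n = 20 (assumed lower return): 2.093 / 4.472 = 0.47 SD
- n = 10 (one subset of the size in section 11.2): 2.262 / 3.162 = 0.72 SD

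Mean change does not do the work of the table. A mean near zero fits everyone being stable, and it also fits half improving and half worsening by the same amount. Its merit is that it uses the full score.

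**The case against.** The strongest defence is that the code fits a stated aim. Section 11.2 wants to find which patient subsets are most likely to benefit, and a logistic regression on improvement addresses that directly. This stands. A reader might infer that the two-level code is wrong and should be replaced. The documents do not support that: what is missing is a companion description of worsening.

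A reader might also infer that no QOL estimate is intended beyond the regression. Section 11.2 states such an intent for each subset, so the accurate statement is that no other QOL method is specified.

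It can be said that any two-level code leaves its pooled level unsplit, and that the illustration uses invented counts with 40 complete forms. Both points are fair. With 12 improved out of 40 complete forms, anywhere from 0 to 28 patients (0-70%) could have worsened, but that range is a logical bound, not a likely size of loss. Deaths and missing forms would change the denominator.

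Harm does not go unseen either. Toxicity is graded during and after the study (sections 10.2.2 and 10.3.3) and reviewed on an ongoing basis (section 12.1). This limits the consequence, though graded toxicity is not the patient's own report of QOL.

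Finally, a reader of Appendix IV might infer that the FACT-G would be mis-scored. The form mixes positively and negatively worded items, the protocol states no scoring rule, and the item on sex life carries the instruction "If you prefer not to answer it, please mark this box". The documents do not support the inference. Appendix IV is a sample of a named, versioned instrument, and nothing says that the items would be summed as printed. A scoring reference would be tidy, but its absence is not a fault in the analysis.

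**Conclusion.** The point holds as a minor gap in the pre-specified analysis of a secondary endpoint. Followed as written, section 11.3 cannot distinguish preserved from worsened QOL, and this falls short of the monitoring purpose in section 1.0. That conclusion rests on the plain meaning of the two labels and on no other QOL method being specified; it does not depend on the assumed counts. The 10% and 60% worsened shares show what the code could hide and do not predict what the trial will find.

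A stronger reading, that the trial will be unable to assess deterioration, is not supported. Forms are collected before therapy and repeatedly afterwards, so the information will exist for patients who return them. The primary objective and the sample size of 44 are unaffected. The reason to act before analysis is that thresholds and visits chosen once results are known would be open to selection.

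**What to change.** Keep the planned logistic regression in section 11.3, and state the threshold and visit that define improvement. Add two items:

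- **(a) A three-category table.** Report improved, stable and worsened at the 6-week visit and at one later scheduled visit from section 10.3.1. Fix the improvement and worsening thresholds on the FACT-G total before analysis. Show deaths in a separate row, and report form completion among those alive.
- **(b) Mean change from baseline** in the FACT-G total with 95% CI at the same visits, as a complement to (a) and not a substitute for it.

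The later visit matters because section 5.0 ideally places SRS/SBRT before treatment of the primary, so at 6 weeks some patients may still be receiving that treatment.

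The cost is a short change to section 11.3 and slightly more analysis on forms already collected, with no new visits, forms or patients. The downside is limited precision. Even with all 40 forms, mean change is known only to within about 0.32 SD, and subset estimates at 0.72 SD should be read as descriptive. Death and drop-out will restrict interpretation of the later visit, which is why the table should show both.

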12.0 DATA SAFETY AND RECORDING

12.1 Data and Safety Monitoring Plan

Investigators/Sub-investigators, regulatory, CRS management, clinical research coordinators, research coordinators, clinical research associates, data managers, and clinic staff meet regularly in disease center Data Safety Monitoring Boards (DSMB) to review and discuss study data to include, but not limited to, the following:

- **serious adverse events**
- **subject safety issues**
- **recruitment issues**
- **accrual**
- **protocol deviations**
- **unanticipated problems**
- **breaches of confidentiality**

Minutes from the disease center DSMB meetings are available to those who are unable to participate during the scheduled meeting time.

All toxicities encountered during the study will be evaluated on an ongoing basis

according to the NCI Common Toxicity Criteria Version 4.0. All study treatment associated adverse events that are serious, at least possibly related and unexpected will be reported to the IRB. Any modifications necessary to ensure subject safety and decisions to continue, or close the trial to accrual are also discussed during these meetings. If any literature becomes available which changes the risk/benefit ratio or suggests that conducting the trial is no longer ethical, the IRB will be notified in the form of an Unanticipated Problem submission and the study may be terminated.
All study data reviewed and discussed during these meetings will be kept confidential. Any breach in subject confidentiality will be reported to the IRB in the form of an Unanticipated Problem submission. The summaries of these meetings are forwarded to the UPMC Hillman Cancer Center DSMC which also meets regularly following a designated format.
For all research protocols, there will be a commitment to comply with the IRB's policies for reporting unanticipated problems involving risk to subjects or others (including adverse events). DSMC progress reports, to include a summary of all serious adverse events and modifications, and approval will be submitted to the IRB at the time of renewal.
Protocols with subjects in long-term (survival) follow-up or protocols in data analysis only, will be reviewed bi-annually.
Both the UPMC Hillman Cancer Center DSMC as well as the individual disease center DSMB have the authority to suspend accrual or further investigate treatment on any trial based on information discussed at these meetings.
All records related to this research study will be stored in a locked environment. Only the researchers affiliated with the research study and their staff will have access to the research records.

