12.2.2 Abnormal Test Findings

An abnormal test finding will be classified as an adverse event if one or more of the following criteria are met:

- The test finding is accompanied by clinical symptoms.
- The test finding necessitates additional diagnostic evaluation(s) or medical/surgical intervention; including significant additional concomitant drug treatment or other therapy.

Note: simply repeating a test finding, in the absence of any of the other listed criteria, does not constitute an AE.

- The test finding leads to a change in study dosing or discontinuation of subject participation in the clinical study.
- The test finding is considered an AE by the Sponsor-Investigator of the IND application.

REPORTING OF SERIOUS ADVERSE EVENTS

All events meeting the definition of a serious adverse event, which occur after the date of first dose of study treatment and within **30** days of the last dose of study treatment, should be reported according to the departmental SAE checklist and SAE form. The initial SAE form should be sent to the following within 24 business hours / 1 business day of the Principal Investigator becoming aware:

1. Investigator: [contact]
2. [contact]
3. Local Institutional Review Board when reporting requirements are met.

In addition to completing appropriate patient demographic and suspect medication information, the report should include as applicable the following information that is available at the time of report within the Sections B and C of the departmental SAE form:

- CTCAE term(s) and grade(s)
- current status of study drug
- all interventions to address the AE (testing and result, treatment and response)

- hospitalization and/or discharge dates
- event relationship to study drug

Follow-up reports:

Additional information may be added to a previously submitted report by adding to the original departmental SAE form and submitting it as follow-up or creating supplemental summary information and submitting it as follow-up with the original departmental SAE form.

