12.2.3 Reporting adverse events to the responsible IRB

In accordance with applicable policies of the University of Pittsburgh Institutional Review Board (IRB), the Investigator will report, to the IRB, any observed or volunteered adverse event that is determined to be 1) associated with the investigational drug or study treatment(s); 2) serious; and 3) unexpected. Adverse event reports will be submitted to the IRB in accordance with the respective IRB procedures.

Applicable adverse events will be reported to the IRB as soon as possible and, in no event, later than 10 calendar days following the investigator's receipt of the respective information. Adverse events which are 1) associated with the investigational drug or study treatment(s); 2) fatal or life-threatening; and 3) unexpected will be reported to the IRB within 24 hours of the Sponsor-Investigator's receipt of the respective information. Follow-up information to a reported adverse event will be submitted to the IRB as soon as the relevant information is available. If the results of the Investigator's follow-up investigation show that an adverse event that was initially determined to not require reporting to the IRB does, in fact, meet the requirements for reporting; the Investigator will report the adverse event to the IRB as soon as possible, but in no event later than 10 calendar days, after the determination was made.

REFERENCES

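### Acceptable toxicity is a primary endpoint, but the plan gives no tolerable Grade 4-5 rate, no toxicity analysis, and no count that obliges a review pause

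*Combined protocol and SAP*

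**What the plan says.** Toxicity is one of two primary endpoints. The Summary, Section 2.0 and Section 11.0 all define it as "Acceptable toxicity: Grade 3 or less". No rate, attribution or time window is attached.

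The rest of Section 11 deals with other outcomes. Section 11.2 takes about 10 patients per primary-cancer subset "in order to have a reasonable estimate of overall survival, local control, and quality of life for each subset". Section 11.3 opens with "Two-year survival rate will be calculated for all the patients and each patient subset respectively", then covers prognostic modelling of survival, quality of life and descriptive statistics. It contains no toxicity analysis.

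Oversight is in Section 12. Under 12.1, "All toxicities encountered during the study will be evaluated on an ongoing basis", the boards meet regularly, and "decisions to continue, or close the trial to accrual are also discussed during these meetings". Both the cancer-center DSMC and the "individual disease center DSMB have the authority to suspend accrual or further investigate treatment on any trial based on information discussed at these meetings". On serious adverse events: "The initial SAE form should be sent to the following within 24 business hours / 1 business day" of the principal investigator learning of the event. Under Reporting adverse events to the responsible IRB, treatment-associated events that are "2) fatal or life-threatening; and 3) unexpected will be reported to the IRB within 24 hours", and other associated, serious, unexpected events within 10 calendar days. Sections 10.2.2 and 10.3.3 require CTCAE grading during and after the study.

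**The concern.** A grade cut classifies one patient. A trial-level verdict also needs the proportion of patients who may exceed the cut, and the plan never gives it. Followed as written, the trial would finish with a list of graded events and no agreed way to say whether its primary safety endpoint was met. Section 1.0 describes the aim as feasibility ahead of a possible phase III study, so that verdict matters.

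The same gap carries into monitoring. With no limit, there is nothing from which to derive a stopping count, and whether frequent Grade 4-5 toxicity leads to a pause depends on the boards' judgement at the time. The disease-center DSMB described in 12.1 includes the investigators and study staff, which makes a criterion fixed in advance more useful.

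**Working it through.** **Step 1: the plan's own figure.** Section 11.2 gives 40 patients plus 10% drop-out: 40 × 1.10 = 44, which reproduces. (Dividing instead, 40 / 0.90 = 44.4, gives 45; the difference is immaterial here.) The 40 rests on about 10 per subset for survival, local control and quality of life. No toxicity rate, error level or power enters, so there is no toxicity figure to reproduce.

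**Step 2: the endpoint read as zero tolerance.** The chance of at least one Grade 4-5 patient among 40 is 1 − (1 − p)^40.
- p = 5%: 1 − 0.95^40 = 0.871
- p = 10%: 1 − 0.90^40 = 0.985

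This reading fails almost regardless of how safe the treatment is.

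**Step 3: the endpoint read loosely.** Exact (Clopper-Pearson) 95% intervals for x of 40:
- 0/40: 0% to 8.8%
- 1/40: 0.1% to 13.2%
- 4/40: 2.8% to 23.7%
- 8/40: 9.1% to 35.6%

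The plan does not say which of these would be acceptable. The form of the success criterion also matters. Requiring the upper limit to lie below 10% would allow only 0/40, which is zero tolerance again.

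**Step 4: an example trigger.** The plan gives no limit, so 10% is assumed throughout.

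*Rule A.* Beta(0.5, 0.5) prior; pause if the posterior probability that the rate exceeds 10%, from Beta(0.5 + x, 0.5 + n − x), is above 0.90. Smallest x:
- n = 10: x = 3 (0.969; x = 2 gives 0.857)
- n = 20: x = 4 (0.922; x = 3 gives 0.786)
- n = 30: x = 6 (0.956; x = 5 gives 0.884)

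*Rule B.* Smallest x with P(X ≥ x | n, 0.10) ≤ 0.05: 4/10 (0.013), 5/20 (0.043), 7/30 (0.026).

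The chance of a pause comes from an exact binomial recursion that removes paths crossing the boundary at each look. For Rule A at a true 20%, the first crossing is at 10, 20 or 30 patients with probability 0.322 + 0.288 + 0.078 = 0.688.

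| True rate | A: 3/10, 4/20, 6/30 | B: 4/10, 5/20, 7/30 |
|---|---|---|
| 5% | 2% | 0.3% |
| 10% | 17% | 6% |
| 15% | 43% | 22% |
| 20% | 69% | 48% |
| 30% | 95% | 87% |

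**Step 5: late events.** The table assumes that every event is known at each look. If a fraction f is known, the rate seen is f × p. At a true 20%:
- f = 0.75 gives 15%, so the pause chance is 43% (A) or 22% (B)
- f = 0.50 gives 10%, so it is 17% or 6%

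**Step 6: what is counted.** Section 5.0 adds surgery, chemotherapy or radiation to the primary, and 7.2 allows later chemotherapy. Suppose SRS/SBRT causes 5% and the other therapy another 10%. Counting all 15% gives a pause chance of 43% (A) or 22% (B). Counting only SRS/SBRT-related events gives 2% or 0.3%. Attribution therefore has to be recorded, and the causality scale in 12.3 rates radiation and drugs together.

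**Step 7: why no look at 40.** At most 44 − 40 = 4 patients could still be protected. Adding 7/40 to Rule A raises the pause chance at a true 20% from 69% to 79%, for almost no benefit.

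**The case against.** The strongest reply is that much of this is form. Two boards already review safety, may suspend accrual, and see serious events quickly. A reader might infer from the missing count that the trial is unmonitored. The documents do not support that: Section 12 is a working oversight system, and only a fixed trigger is absent. This limits the weight of the trigger but does not answer the endpoint gap, since discretion to suspend accrual does not supply a criterion for the final result.

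Second, the cited data point to low rates. Section 1.0 reports 2 of 29 patients with Grade 3 or higher in a prospective trial of one to five sites (6.9%, exact 95% CI 0.8% to 22.8%) and 2% Grade 3 in a 50-patient lung series. Even if the 6.9% were all Grade 4-5, Rule A would pause with probability 6% and Rule B with 1%. The 30% row lies above the upper confidence limit. This stands. A reader might also infer that the regimen has no safety background; Section 1.0 says only that, to the authors' knowledge, no prospective trial was confined to initial presentation.

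Third, the counts depend on choices. With the same 10% limit and 0.90 cutoff (reached or exceeded) but a Beta(0.2, 1.8) prior, the boundaries become 3/10, 5/20 and 6/30, and the pause chance at 20% is 63%. This stands too: the recommendation is to set a limit and derive a rule, not to adopt particular counts.

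Fourth, pooling Grades 4 and 5 means that two related deaths in the first 10 patients would not reach 3/10. That is correct, and the fix handles Grade 5 separately.

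Finally, a reader might turn the pause chances into a number of severe events avoided. The documents do not support that step. The boards may act on their own, enrolment continues while a look awaits its last patient's visit, and no accrual rate is given.

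**Conclusion.** The concern holds in two parts. The firmer one is that a primary endpoint has no trial-level criterion and no analysis. This follows from the text of Section 11 and needs no assumption: the plan as written cannot return a verdict on it. The second is that Section 12.1 grants authority to suspend accrual but sets no count that obliges a review pause. That is a narrower gap in real oversight.

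The size of the second part rests on assumptions: a 10% limit, independent patients with a common rate, three looks, and all events known at each. With Rule A, a pause has a 2% chance at a true 5% and 69% at 20%. Late events lower these figures, and enrolment while waiting for the 6-week visit lowers the benefit of a pause. If severe SRS/SBRT toxicity is rare, the trigger changes almost nothing. This is a cheap improvement, not evidence that patients are unprotected.

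**What to change.** **Sections 11.0 and 11.3.** State a tolerable proportion of patients with Grade 4-5 toxicity at least possibly related to SRS/SBRT. The sponsor sets it; 10% is only illustrative. Report the proportion among patients given at least one SRS/SBRT fraction, with an exact 95% CI and a stated success criterion against the limit. Choose that criterion with Step 3 in view, so that it does not become zero tolerance by accident.

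**Section 12.1.** Add a review pause for the existing DSMB and DSMC, derived from that limit, at 10, 20 and 30 treated patients. For a 10% limit this could be 3/10, 4/20 and 6/30, or 4/10, 5/20 and 7/30 for fewer unneeded pauses.
- Hold each look when the last of those patients has reached the 6-week visit in 10.3.1, or has died or left the study before it.
- Count from the CTCAE evaluations in 10.2.2 and 10.3.3 up to that visit, plus later related events known at the look. Do not rely on SAE forms alone, because their window closes 30 days after the last dose of study treatment.
- Exclude disease progression and events attributed only to primary or later systemic therapy.
- Any Grade 5 event at least possibly related to SRS/SBRT prompts immediate board review.
- Accrual may resume after review, and the boards may always act earlier.
- State the pause chances with the late-event and enrolment caveats.

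**Section 12.3.** For each Grade 4-5 event, record whether it is at least possibly related to SRS/SBRT.

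**Cost.** A short amendment, one attribution item per Grade 4-5 event, and a running count at meetings already held. No new committee, visits or patients are needed. The downside is an occasional unneeded but resumable pause: at a true 5%, 2% (A) or 0.3% (B); at exactly 10%, 17% or 6%.
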